## PROTOCOL TITLE: COPD Helpline study

### 1.0 Purpose of the Study:

Chronic Obstructive Pulmonary Disease (COPD) is an increasingly prevalent and costly chronic health condition, and is the third major cause of morbidity and mortality in the United States. Self-management treatment programs for COPD are shown to improve health-related quality of life and prevent COPD-related hospitalizations. Despite their clinical benefits, these programs are typically multi-component and time- and resource-intensive. To date, no study has been conducted to isolate the role of individual self-management treatment components in contributing to improved COPD outcomes. The proposed research will establish the feasibility of using the Multiphase Optimization Strategy (MOST) framework to optimize COPD self-management treatment delivered by the American Lung Association (ALA) Helpline. Treatment components to be evaluated include duration of self-management education, ground-based walking training, inhaler training, and caregiver support. The primary outcome is health-related quality of life, with secondary outcomes of COPD symptom burden, self-management behaviors, and hospitalization. Specific aims are:

**Aim 1: Design a factorial experiment and develop operational procedures.** We will design a factorial experiment with the same number of experimental conditions and length of follow-up as the planned optimization trial. In collaboration with the ALA COPD Helpline, we will develop operational procedures (i.e., recruitment, screening, randomization, and database management) for successful implementation.

**Aim 2: Establish feasibility and acceptability by pilot testing the study design.** We will deliver treatment to three participants per experimental condition ( $N=48$ ) with good fidelity, and will remotely assess baseline, mediator, and outcome variables. We will conduct qualitative interviews at end-of-treatment with 15-20 participants. Resulting values will provide estimates of recruitment and retention rates, treatment fidelity, acceptability of treatment components, and outcome measure variability to inform a subsequent, fully-powered optimization trial. The primary outcome is health-related quality of life, with secondary outcomes of COPD symptom burden, self-management behaviors, and hospitalization.

### 2.0 Background / Literature Review / Rationale for the study:

**Chronic Obstructive Pulmonary Disease (COPD) is an increasingly prevalent and costly chronic health condition.** COPD is a chronic, progressive disease that is the third major cause of morbidity and mortality in the United States. Whereas mortality from most common causes of death such as cardiovascular disease and cancer has declined over the past 40 years, mortality attributable to COPD has doubled. COPD is responsible for more than 2.7 million deaths and 50 billion dollars of healthcare expenditure in the U.S. every year.

**Self-management treatment improves COPD functioning.** A recent Delphi process has resulted in the conceptual definition for COPD self-management treatment as structured but personalized and often multi-component, with goals of motivating, engaging, and supporting patients to positively adapt health behaviors and develop skills to better manage their disease. COPD self-management treatment has a dual focus on reducing current symptoms and reducing future exacerbation risk. Programs typically include components focused on COPD education, recognition and treatment of exacerbations, dyspnea management, correct device use, smoking cessation, physical activity, nutrition, social support, and treatment of comorbidities.

Over the past 20 years, numerous randomized clinical trials (RCTs) have shown self-management treatment to have robust effects on improving health-related quality of life in COPD. Self-management treatment also improves dyspnea, decreases emergency department visits, and prevents up to 40% of COPD-related hospitalizations. Findings on mortality are mixed; two recent high-quality trials have demonstrated decreased mortality risk, while a 2017 Cochrane review detected a small, but statistically significant, higher respiratory-related mortality rate in the self-management group as compared to usual care. Authors suggest caution in interpreting this finding, as the overall effect was dominated by two studies,

[figure not shown]
## PROTOCOL TITLE: COPD Helpline study

misclassification in cause of death is common, and no effect on all-cause mortality was seen in the overall analysis. Given the overarching evidence of treatment benefit, self-management treatment is proposed in a chronic care model of COPD and recommended in international COPD guidelines.

**There is a need to optimize COPD self-management treatment.** To date, there have been several attempts to characterize the effective elements of COPD self-management treatment; however, findings have been greatly limited due to program heterogeneity. Jonkman and colleagues (2016) conducted an individual patient data meta-analysis which identified intervention duration as the sole effect modifier. This study design was unable to assess whether negative findings were due to methodological limitations of the meta-analysis, lack of fidelity of intervention delivery, heterogeneous groups of studies being compared, or other sources of variability. Raymond and colleagues (2019) determined that attempts to identify beneficial components were confounded by intervention complexity and heterogeneity, such that the optimal content of COPD self-management treatment cannot be defined from the currently published literature.

Novel experimental approaches could help to address this critical research gap and optimize the effectiveness of multi-component COPD self-management interventions on health-related quality of life. The Multiphase Optimization Strategy (MOST) framework is an innovative, engineering-inspired methodological framework for intervention development (Figure 1) that uses highly efficient randomized experimentation to assess the performance of individual intervention components and their interactions on clinically-relevant outcomes. The MOST framework can be used to systematically identify the most promising intervention components, and interactions of components, that drive the effect of self-management treatment on COPD outcomes. The MOST framework can also identify any treatment component, or combination of components, with unintended harmful effects (i.e., inappropriate management strategies for an exacerbation), so that these components can be eliminated from future treatment programs. Thus, MOST is ideally suited to address the significant clinical problem of heterogeneity among self-management programs, and has strong potential to advance the field of self-management treatment for COPD. In the proposed project, we seek to establish the feasibility of using the MOST framework to optimize treatment delivered by the American Lung Association (ALA) Helpline.

**Figure 1. MOST Framework**

### 3.0 Inclusion and exclusion criteria:

Study eligibility will be determined as follows: Inclusion criteria: Eligible participants will be males and females who are 1) 40 years or older, 2) report a physician diagnosis of COPD, 3) use an inhaler for COPD at least once a week, 4) able to walk at least one block without assistance, 5) able to identify a caregiver, and 6) have access to a connected device (i.e., smart phone, tablet, and/ or computer). Participants will be excluded in the presence of any of the following. Exclusion criteria: 1) cognitive dysfunction impairing ability to provide informed consent and follow study procedures, 2) terminal illness (i.e. less than 6 months life expectancy) that is non-COPD related, 3) living at a chronic care facility (i.e. nursing home, assisted living), or 4) inability to speak and read English.

We will not include adults unable to consent, pregnant women, prisoners, or individuals under the age of 18. Socioeconomically disadvantaged persons will be included in this study, but not targeted for recruitment.

## PROTOCOL TITLE: COPD Helpline study

**4.0 Procedures Involved:****Overall Study Design**

In the proposed project, we seek to establish the feasibility of using the Multiphase Optimization Strategy (MOST) framework to optimize treatment delivered by the American Lung Association (ALA) Helpline. MOST is an innovative, engineering-inspired methodological framework for intervention development that uses highly efficient randomized experimentation to assess the performance of individual intervention components and their interactions on clinically-relevant outcomes.

**Factorial study design.** We will conduct a randomized factorial experiment to examine the effects of four interventions components (Figure 2), in preparation for a full-scale optimization trial. Randomization will be stratified by current smoking status. Each treatment condition corresponds to a factor with two possible levels, resulting in a total 16 experimental conditions (Table 1).

**Participants.**

[figure not shown]
The randomized factorial experiment will consist of 48 participants. We will partner with the American Lung Association (ALA) Illinois chapter team and recruit participants from the ALA COPD Helpline for this study, following recruitment procedures described below. The PI has collaborated with the ALA-Illinois chapter team since 2015, and the proposed research is a natural extension of this partnership. As the ALA Living Well with COPD programs reaches over 800 callers per year, we believe that accrual targets (4 participants/ month; planned N=48) will be feasible in the grant period.

**Procedures.** We will conduct a pilot randomized factorial trial in which participants will be randomized to one of two levels for each of the four intervention components. This will result in a total of 16 study conditions, 3 participants per condition (N=48).

**Length of participation.** As shown in Figure 4, participants will be enrolled in the study for approximately 4 months (14 weeks).

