## PROTOCOL TITLE: COPD Helpline study

Consenting procedures will follow Rush IRB guidance for the use of electronic informed consent, described below.

Following consent, participants will be sent a baseline survey link by text message or email, or given the option to complete the baseline survey by phone interview format. After baseline survey completion, participants will be randomized to treatment following a randomization scheme programmed in REDCap. Participants will be mailed study materials specific to their treatment condition, consisting of the “Living Well with COPD” booklet and treatment material for up to three other treatment components.

Participants will be assigned to one of 16 possible experimental conditions, consisting of self-management education (either short or long duration) and up to three additional treatment components. The study schedule for each treatment condition is depicted in Figure 4. Self-management education will be delivered by an ALA Helpline counselor who is a certified COPD educator. Inhaler education will be delivered by a trained interventionist (advanced Respiratory Therapy student), overseen by the PI. Ground-based walking training and caregiver support will be delivered by a trained study staff member. All questionnaire assessments will be administered remotely through the REDCap data management system. Study staff will follow up with the participant to ensure all measures are completed, and address any questions or technical issues. Lastly, a subset of 15-20 participants will be invited to participate in a qualitative interview at end-of-treatment.

**Baseline Assessment (Week 0).** Prior to randomization, participants will complete a questionnaire battery of socio-demographic information, COPD-related measures, potential treatment mediators, and smoking-related measures, if applicable, as described below.

**Mid-treatment Assessment (Week 5).** Participants will complete a questionnaire battery of potential treatment mediators and adverse events, as described below.

[figure not shown]

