**End-of-treatment Assessment (Week 8).**

Participants will complete a questionnaire battery of COPD-related measures, potential treatment mediators, and smoking-related measures, if applicable, as described below. Participants who were invited to participate in a qualitative interview will complete it at this stage.

[figure not shown]
**90-day follow up (Week 14).** Approximately 90 days after treatment start date, participants will complete a final questionnaire battery of COPD-related measures and smoking-related measures, if applicable, as described below.

**Intervention components.** Our selection of intervention components is based on recent, high-quality meta-analyses and international considerations: intervention components considered for inclusion in an optimized treatment package. Although patient education forms the ‘core’ of self-management treatment, education alone is insufficient to foster health behavior change. Instead, self-management treatment should be individually tailored and employ structured behavior change techniques.

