## PROTOCOL TITLE: COPD Helpline study

management behaviors, and hospitalization. COPD symptom burden will be assessed with the COPD Assessment Test (CAT), an 8-item questionnaire measuring the global impact of dyspnea on health status. Self-management behaviors will be assessed with the Patient Activation Measure (PAM-13), a 13-item questionnaire measuring patient knowledge, skill, and confidence for self-management. Self-reported hospitalization history will be assessed by asking participants if they have been hospitalized for their COPD (i.e., respiratory-related hospitalization) or other medical conditions (i.e., all-cause hospitalization) since enrolling in the study. Lastly, we will monitor for adverse events at all assessment timepoints, as described in the Data and Safety Monitoring Plan.

**Treatment mediators.** COPD knowledge will be assessed with the Bristol COPD Knowledge Questionnaire. Physical activity will be assessed with the International Physical Activity Questionnaire (IPAQ). Inhaler confidence will be assessed with the Inhaler Confidence Scale. Informational support will be assessed with the PROMIS Informational Support scale.

**Treatment acceptability.** We will assess treatment acceptability with the 8-item Client Satisfaction Questionnaire (CSQ-8), with adequate acceptability indicated by a total score of 24/30 or greater. To complement the CSQ-8, we will conduct qualitative interviews at end-of-treatment with a subset of approximately 15-20 participants, until thematic saturation is reached (i.e., the point at which each subsequent interview provides no new information). Qualitative interview content will focus on perceived benefits of treatment, treatment burden and other negative aspects of treatment, and suggestions for improving COPD self-management treatment. We will use a purposive sampling approach to ensure the sample is balanced by gender, race/ ethnicity, and exposure to each of the four treatment components. Following independent reviews of transcripts by the PI and trained research staff, and identification of *a priori* and in-vivo themes, initial codes will be assigned with content and comparative analysis using QSR NVivo version 11 software.

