**Analytic Strategy.** Three main areas will be examined: 1. Feasibility of recruitment and outcome procedures. Feasibility will be evaluated via enrollment ratios, monthly recruitment rates, retention rates, and data completeness 2. Feasibility and acceptability of the treatment components. Treatment feasibility will be assessed by treatment fidelity ratings. Treatment acceptability will be assessed with the CSQ-8 in the full sample, and qualitative interviews in a subset of participants. 3. Explore the variability and acceptability of trial outcomes and treatment. We will examine the variability of the change in the COPD-related outcomes and treatment mediator measures. We will examine the proportion of hospitalization events over the course of the study, as well as the proportion of participants who endorse clinically meaningful change from baseline to 90-day follow-up on the CRQ and CAT. We will assess all questionnaires for good measurement properties (i.e., good internal consistency and sensitivity to treatment-related change) prior to selection in the planned optimization trial.

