**Monitoring of Data Quality**

The REDCap database will contain embedded protocols to guide study activities and specify the order of implementation, such that participants receive all the intervention components to which they are assigned and only the intervention components to which they are assigned. Quality assurance checks (i.e., required items, allowable ranges of response values) will be built into each REDCap survey to ensure data accuracy at the time of entry. Erroneous and/or inconsistent values will be flagged and entered into a recurring query report specifically developed for this study. Reports will be generated weekly and distributed to designated study staff for resolution. Once generated, a query will remain part of the weekly report until it is resolved. The PI will receive weekly aggregated reports on study recruitment and follow-up status and study intervention fidelity by treatment component. We will monitor the fidelity to the treatment protocol timeline and percentage of components delivered in each treatment condition. Our study database will also include a scheduling program that tracks when research contacts occur and when visits or calls need to be scheduled based on the participants' condition.

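### Does giving the length of participation as about 4 months (14 weeks) leave the hospitalisation proportion without a usable observation period?

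*Combined protocol and SAP*

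**What the plan says.** Section 4.0, Length of participation, citing Figure 4: "participants will be enrolled in the study for approximately 4 months (14 weeks").

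The assessment schedule in the same section sets Week 0 at baseline: "Prior to randomization, participants will complete a questionnaire battery". Mid-treatment is Week 5 and end of treatment is Week 8. The last assessment is headed "90-day follow up (Week 14") and timed as follows: "Approximately 90 days after treatment start date, participants will complete a final questionnaire battery".

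Hospitalisation is a secondary outcome. Under Outcomes, participants are asked whether they have been hospitalised for COPD or for "other medical conditions (i.e., all-cause hospitalization) since enrolling in the study". Table 2 collects it at baseline, end of treatment and the 90-day follow-up. The Analytic Strategy then says: "We will examine the proportion of hospitalization events over the course of the study".

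Aim 1 in Section 1.0 commits the pilot to the "same number of experimental conditions and length of follow-up as the planned optimization trial". Section 14.0 (Monitoring of Data Quality) describes a database with "a scheduling program that tracks when research contacts occur".

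**The concern.** The sentence on participation equates two durations that differ by more than three weeks. The schedule around it also uses more than one time origin. Study weeks run from a baseline completed before randomisation, the final visit is timed from treatment start, and hospitalisation is counted from enrolment. The readable text does not define treatment start, and Figure 4 could not be read.

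A proportion with at least one hospitalisation means little without the length of time over which it was observed. The pilot values are meant to inform a fully powered optimization trial. If a reader could not tell whether the proportion covered about 98 days, about 122 days, or a period that varied by participant, the planning figure would carry avoidable uncertainty.

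**Working it through.** **1. The stated duration.** Inputs: 14 weeks and 4 months, from Length of participation. A mean calendar month is 365.25 / 12 = 30.44 days.

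- 14 weeks: 14 × 7 = 98 days; 98 / 30.44 = 3.2 months.
- 4 months: 4 × 30.44 = 121.75 days; 121.75 / 7 = 17.4 weeks.
- Ratio: 121.75 / 98 = 1.24; gap 23.75 days.
- With four-week months: 14 / 4 = 3.5 months, and 4 months is 16 weeks (16 / 14 = 1.14).

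The plan's equality is not reproduced under either convention. That part of the concern is correct.

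**2. Which figure the schedule supports.** Inputs: Week 14 from a Week 0 baseline, and about 90 days from treatment start.

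- 90 / 7 = 12.9 weeks.
- The two timings coincide when treatment starts 98 − 90 = 8 days after Week 0. Randomisation and the mailing of materials both follow baseline, so a short lead-in is expected.
- Assumed lags of 0, 8 and 21 days put the final visit at day 90, 98 and 111 after Week 0, that is week 12.9, 14.0 and 15.9.
- For the final visit to fall 4 months after Week 0, treatment would have to start 121.75 − 90 = about 32 days after baseline. Nothing in the documents suggests this.

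The 14-week figure fits the schedule and the 4-month figure does not.

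**3. The hospitalisation window.** The Outcomes text gives the start (enrolment). Table 2 and the 90-day follow-up paragraph give the last collection point. The Analytic Strategy refers to the course of the study and does not use the 4-month figure. A window is therefore stated. It varies somewhat by participant, as any window closing at a scheduled visit does.

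**4. Size if the wrong duration were read.** No hospitalisation rate is given, so constant rates r of 0.25, 0.5 and 1.0 per person-year are assumed. Proportion with at least one event by day d: 1 − exp(−r × d / 365.25). Standard error at 98 days with N = 48: √(p(1 − p) / 48).

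| Assumed rate | 98 days | 121.75 days | Difference | SE at 98 days | Participants of 48 |
|---|---|---|---|---|---|
| 0.25 | 6.5% | 8.0% | 1.5 points | 3.6 points | 3.1 vs 3.8 |
| 0.5 | 12.6% | 15.4% | 2.8 points | 4.8 points | 6.0 vs 7.4 |
| 1.0 | 23.5% | 28.3% | 4.8 points | 6.1 points | 11.3 vs 13.6 |

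Every difference is below one standard error, and this is the extreme contrast. The more realistic one is variation in the start lag. At r = 0.5, day 90 gives 1 − exp(−0.1232) = 11.6% and day 111 gives 1 − exp(−0.1520) = 14.1%, or 5.6 and 6.8 of 48 participants.

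**The case for a change.** The best case for acting is that the wording is wrong on its face and cheap to correct. Allowing for approximation does not help much, since 14 weeks rounds to 3 calendar months. Treatment start could mean the mailing of materials, first pedometer use or the first call, because different staff deliver the components and the walking component opens with a 7-day step count. No visit window is given in the readable text. The plan does not say whether the hospitalisation proportion counts participants or events, or how someone without a final assessment is handled. Hospitalisation is a named secondary outcome, and its estimate is to be carried forward.

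What stands is the unit mismatch and the absence of those reporting details. What does not stand is the step from there to a missing observation period, because both ends of the window are given. The contrast between 98 and 122 days treats a loose rounding as though it were a rival schedule.

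The possible remedies add little. Contact dates are already tracked, so days from enrolment to last completed assessment can be reported without any new rule. Events per unit of person-time would need counts, and the question as described asks only whether a hospitalisation occurred. Nothing in the documents restricts retention to those who start treatment. Since Aim 1 fixes the same length of follow-up for both trials, the pilot proportion carries over to a similar period, whatever label that period is given.

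**Conclusion.** The plan can stand. Describing 14 weeks as about 4 months is a clerical slip that overstates the period by 24% in one descriptive sentence. The visit schedule itself is coherent: Week 14 and about 90 days from treatment start agree with a lead-in of about 8 days. No sample size, test or decision rule depends on the month figure.

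The details left open (the exact day zero, and how incomplete follow-up enters the proportion) are ones an analyst would settle sensibly when reporting, by giving the observed period from enrolment to last completed assessment. Following the plan as written would still give a sound descriptive result in a 48-person feasibility pilot.

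The sizes rest on assumed constant rates of 0.25 to 1.0 hospitalisations per person-year, which are not in the documents. Across that range the largest shift is 4.8 percentage points against a standard error of 6.1. The conversion of weeks to months needs no assumption beyond the length of a month. Figure 4 could not be checked and may already define treatment start.
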